1. INTRODUCTION

1.1 Disease Overview

Constipation in children has similar characteristics to that of constipation in adults in that symptoms include infrequent bowel movements (BMs), hard stools, and painful passage of stools. Children may also experience faecal retention due to withholding.^{1,2} There is a tendency to avoid defecation and withhold BMs due to pain experienced from the passage of large stools. This withholding of BMs can result in episodes of faecal incontinence. Functional constipation occurs in all paediatric age groups, from newborns to young adults and its severity may vary from mild and short-lived to severe and chronic with faecal impaction. It is responsible for 3–5% of paediatric outpatient visits and 25% of paediatric gastroenterology consultations.^{1,2,3} Standardized diagnostic criteria for paediatric functional constipation have been defined by the Rome Committee for Functional Gastrointestinal Disorders.³ Under Rome III, the diagnostic criteria for childhood functional constipation require that children of a developmental age of at least 4 years with insufficient criteria for diagnosis of irritable bowel syndrome (IBS) present with two or more of the following at least once per week for 2 months prior to diagnosis:

- Two or fewer defecations in the toilet per week
- At least one episode of faecal incontinence per week
- History of retentive posturing or excessive volitional stool retention
- History of painful or hard bowel movements
- Presence of a large faecal mass in the rectum
- History of large diameter stools which may obstruct the toilet

One systematic review showed a worldwide prevalence of childhood constipation in the general population ranging from 0.7% to 29.6%.⁴ Similar prevalence rates were reported for boys and girls. Childhood constipation continues beyond puberty in up to one third of the children followed up.⁵ Children aged 2 to 4 years seem to have a higher recurrence rate and a need for prolonged medication and support than younger infants.⁶ One follow-up study has noted increased risk of persistent constipation in children who developed constipation early in infancy and who have a family history of constipation.⁷ Another follow-up study assessing the clinical course of severe functional constipation in early childhood found that after initial success of treatment, a relapse occurred in 15% of the children within 3 years. Symptom duration of 3 months or less before referral was significantly correlated with better outcome.⁸

Medical treatment is aimed at disimpaction of the impacted faeces and restoration of regular bowel habits, which consist of passage of soft, normal stools without discomfort. The administration of laxatives is also used to achieve a normal bowel habit of passing a soft stool without pain. Even though the traditional treatment is well established and safe, for many patients it does not provide a satisfactory improvement, prompting interest in other therapeutic strategies.⁹

1.2 Product Background

Lubiprostone (24-mcg capsules administered twice daily [BID]) is currently approved in the US under the trade name Amitiza® for the treatment of adults with chronic idiopathic constipation and opioid-induced constipation in adults with chronic, non-cancer pain, and for women with irritable bowel syndrome with constipation (8 mcg BID). Lubiprostone 24-mcg BID is also approved for treatment of adult chronic idiopathic constipation in the United Kingdom and Switzerland. Lubiprostone was approved for marketing in Japan on 29 June 2012 for the treatment of chronic constipation (excluding constipation caused by organic diseases) in the adult population. In several well-controlled clinical studies in subjects with chronic idiopathic constipation, opioid-induced constipation or irritable bowel syndrome with constipation, lubiprostone has been shown to increase the frequency of spontaneous bowel movements (SBMs) in adults, to improve stool consistency, and to reduce straining, abdominal bloating, and abdominal discomfort.¹⁰ An open-label safety and efficacy study of 4 weeks' duration has also been conducted in paediatric functional constipation subjects aged 3-17 years who were treated with lubiprostone 12 mcg once daily (QD), 12 mcg BID, or 24 mcg BID and improvement in SBM frequencies were reported in all dose groups.¹¹

1.2.1 Preclinical information

A full summary of the findings from all non-clinical studies can be found in the current Investigator Brochure.

1.2.2 Clinical information

A full summary of previous clinical studies with lubiprostone, known and potential side effects can be found in the current Investigator Brochure.

1.3 Rationale for Study

Even though traditional treatment of functional constipation in children is available and safe, for many patients it does not provide a satisfactory improvement, prompting interest in other therapeutic strategies. Since lubiprostone has been shown to increase the frequency of SBMs in both adults and children, further evaluation in well controlled studies in children is needed to demonstrate use in a paediatric population. The doses selected for this study are based on the results obtained during the previous open-labeled study in children.¹² Highly statistically significant ($p < 0.0001$) changes from baseline SBM frequency at Week 1 were observed overall for children treated with lubiprostone, with children treated with either lubiprostone 12 mcg BID or 24 mcg BID achieving a mean SBM frequency of > 3 SBMs following one week of treatment with lubiprostone. The greatest Week 1 improvement was observed for the lubiprostone 24 mcg BID group. Results from this study also suggested that allowance for dose escalation in some subjects initially dosed with 12 mcg BID may have provided some additional treatment benefits.

Subjects who completed the entire 12-week treatment in the preceding double-blind study (SAG/0211PFC-1131) will be eligible to enrol into this long-term safety study. Dose assignment will be based on the dose they were receiving at the time of rolling over from the previous study into this safety extension study for those subjects who were randomised to receive lubiprostone during the preceding study. For subjects who received placebo during the preceding study,

assignment of dose will be assigned based on subject body weight at the time of rollover to this extension study. All dose assignment will be handled by an Interactive Voice/Web Response system (IXRS) and will continue to maintain blinding with respect to the treatment assignment in the preceding trial.

Lubiprostone has a well-documented safety record in clinical studies involving over 3,500 subjects. The safety record, along with previously observed improvement in constipation signs and symptoms in both children and adults, provides a potential treatment option in a paediatric population.

2. STUDY OBJECTIVES AND ENDPOINTS

2.1 Objectives

To assess the long-term safety, efficacy, and pharmacokinetics of oral lubiprostone 12 or 24 mcg capsules dosed twice daily (BID) when administered orally for 36 weeks in paediatric subjects with functional constipation. Evaluation of lubiprostone safety is the primary objective in this study.

2.2 Endpoints

2.2.1 Safety

The safety endpoints are as follows:

- Incidence of adverse events grouped by MedDRA System Organ Class (SOC) and Preferred Term
- Changes from baseline in clinical laboratory parameters (haematology, serum chemistry, urinalysis)
- Changes from baseline in physical examination
- Changes from baseline in vital sign measurement, including height, and weight
 - Height will be measured using a wall-mounted stadiometer, if available
- For those subjects who were aged 6 to 9 or 14 to 17 at the time of enrolment into the SAG/0211PFC-1131 study, and who were qualified to participate and enrolled in the DXA substudy:
 - Percent changes from baseline in BMD and BMC
 - Changes from baseline in BMD Z-scores and in height-adjusted Z-scores, as assessed by DXA for DXA Subgroup
 - Changes from baseline in height and weight Z-scores
 - Incidence of clinical fractures

A DSMB will monitor safety data on a regular basis throughout the study. Specifics, including meeting frequency and stoppage criteria, are provided in the DSMB Charter.

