
Safety Endpoints:
	
The safety endpoints are as follows:
 
 • Incidence of adverse events (AEs) grouped by MedDRA System Organ Class (SOC) and Preferred Term • Changes from baseline in clinical laboratory parameters (haematology, serum chemistry, urinalysis) • Changes from baseline in physical examination • Changes from baseline in vital sign measurements, including height and weight 
 ○ Height will be measured using a wall-mounted stadiometer, if available • For those subjects who were aged 6 to 9 or 14 to 17 at the time of enrolment into the SAG/0211PFC-1131 study, and who were qualified to participate and enrolled in the dual-energy X-ray absorptiometry (DXA) substudy: 
 ○ Percent changes from baseline in bone mineral density (BMD) and bone mineral content (BMC) ○ Changes from baseline in BMD Z-scores and in height-adjusted Z-scores, as assessed by DXA for DXA Subgroup ○ Changes from baseline in height and weight Z-scores for DXA Subgroup ○ Incidence of clinical fractures 
A Data Safety Monitoring Board (DSMB) will monitor safety data on a regular basis throughout the study. Specifics, including meeting frequency and stoppage criteria, are provided in the DSMB Charter.

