Physical Examination – A complete physical examination of the subject will be performed by appropriate site personnel. Physical examination findings should correlate with the subject's medical history and current diagnosis.

Abbreviated Physical Examination – An abbreviated physical examination of the subjects will be performed by appropriate site personnel. This examination reviews only those body systems where there has been a change in health or there is new finding to report.

Laboratory Tests – Urine and blood samples will be collected and sent to a central laboratory for analysis (see [Section 6.3](#) for details). Age-appropriate normative clinical laboratory values, based on the clinical laboratory's paediatric ranges, will be used to determine abnormal laboratory values for this study.

Pregnancy Test – All female subjects of childbearing potential will have a urine pregnancy test performed at all clinic visits. Childbearing potential will be defined as any female subject who has reported first menses.

Pharmacokinetic Evaluations – Sample collections for the determination of lubiprostone and metabolite M3 concentrations will be performed in all subjects.

Bone Growth Assessments – For those subjects who were aged 6 to 9 or 14 to 17 at the time of enrolment into the SAG/0211PFC-1131 study, and who were qualified to participate and enrolled in the DXA substudy, BMD and BMC measurement using DXA will be performed at Month 9 (Visit 16). All subjects who withdraw from the study after Visit 12 (Month 3) should complete the final visit of the treatment period (Visit 16) and therefore have a final DXA assessment performed. This will only be required for subjects that were originally part of the DXA subgroup. Analysis of scans will be performed by a central reader.

Any subject demonstrating a decline in 4% in BMD at any skeletal site from Screening to End of Treatment should additionally undergo a follow-up DXA assessment 6 to 12 months later.

Adverse Events – AEs will be reported by the subject from the time of informed consent through the end of the follow-up period. AEs will be followed by the Investigator as determined by Sponsor or designee. Further details on AE reporting are provided in [Section 7](#).

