6.3 Safety Evaluations

The following safety evaluations will be performed during the study to measure the safety of the study medication:

Adverse Events: AEs will be reported by the subject from the time of informed consent through the end of the follow-up period. AEs will be followed by the Investigator as determined by Sponsor or designee. Further details on AE reporting are provided in [Section 7](#). Any study medication related AEs persisting at the end of the study will be followed until resolution, or until a clinically stable endpoint has been reached.

In this study, faecal impaction and bone fractures will be captured as AEs. The events of faecal impaction will be used for the analysis of the fecal impaction frequency during the study (see [Section 8.6.2.5](#)).

Clinical Laboratory Tests: The following laboratory tests will be conducted and the appropriate Investigator shall determine the clinical significance of any out-of-range values.

- **Hematology Panel:** Hemoglobin, hematocrit, MCV, MCH, MCHC, RBC, WBC, white blood cell with absolute counts and percent differentials (neutrophils, lymphocytes, monocytes, eosinophils, basophils), platelet count.
- **Chemistry Panel:** Total cholesterol, triglycerides, glucose, total protein, albumin, alkaline phosphatase, AST, ALT, GGT, iron, LDH, total bilirubin, direct bilirubin, BUN, uric acid, creatinine, sodium, potassium, chloride, bicarbonate, calcium, phosphorus, magnesium.
- **Urinalysis:** Protein, glucose, ketones, occult blood, pH, specific gravity, color, appearance, leukocyte esterase, nitrite, bilirubin, and macroscopic examination. Microscopic examination will be done if abnormalities are present. Urine samples will be collected, when possible.

Physical Examination: Physical examinations will be conducted at various timepoints during the study. Any new post treatment findings or changes, as noted by the Investigator, will be reported as an AE.

Vital Signs:

Vital signs (including height and weight at designated visits) will be recorded during the study. Any post treatment clinically significant changes in vital signs (including weight) shall be noted by the Investigator and reported as an AE. Additional guidance regarding assessment of changes in blood pressure and heart rate are provided below.

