8.5.6 Vital Signs

Descriptive statistics will be provided to evaluate the changes from baseline for any vital signs, including height and weight, measured during the study.

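### Height and weight Z-scores and the dedicated fracture endpoint are limited to DXA substudy participants, although neither needs a scan and the source data are collected in every subject

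*Combined protocol and SAP*

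**What the plan says.** One bullet among the safety endpoints in protocol section 2.2.1 applies to a restricted group. It begins "For those subjects who were aged 6 to 9 or 14 to 17 at the time of enrolment into the SAG/0211PFC-1131 study" and continues "and who were qualified to participate and enrolled in the DXA substudy". Four items are nested under it: percent change in BMD and BMC; change in BMD Z-scores and height-adjusted Z-scores; "Changes from baseline in height and weight Z-scores"; and "Incidence of clinical fractures". The synopsis (Safety Endpoints) has the same nesting and spells out the restriction in the growth item: "Changes from baseline in height and weight Z-scores for DXA Subgroup". Section 8.5.5 again places height and weight Z-scores in the DXA subgroup. It does not list fractures.

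The source data are wider than the subgroup. Section 6.3 says "In this study, faecal impaction and bone fractures will be captured as AEs", with no limit by age or substudy. The Schedule of Evaluations has height and weight for all subjects at Visit 9 (taken from Visit 7 of the preceding study) and at Visits 10, 12, 14, 16 and 17.

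Two analyses cover everyone. Section 8.5.6 states: "Descriptive statistics will be provided to evaluate the changes from baseline for any vital signs, including height and weight, measured during the study". Section 8.5.2 tabulates adverse events by system organ class and preferred term, and section 8.2 defines the Safety population as all enrolled subjects who are dosed.

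Section 9.3.3 gives the only reason for the two age cohorts: to keep down the number of children who undergo DXA scans.

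**The concern.** Safety is the primary objective (section 2.1), and growth and bone are the paediatric-specific parts of it. The reason for restricting the age cohorts applies to the scan. It does not apply to a Z-score computed from height, weight, age and sex, or to a count of fractures.

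The growth endpoint is the more serious of the two. Outside the substudy the plan gives only raw change in height and weight over 36 weeks. All subjects receive lubiprostone and nobody is randomised (section 5.5.2), so no control group shows what normal growth would have been. Children gain height and weight anyway, so a positive mean change is what one would see with normal growth and also with moderately slowed growth. A Z-score supplies the missing age- and sex-specific reference.

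For fractures the gap is smaller. The events are tabulated for everyone, but no analysis section defines a single grouped fracture incidence for any population, and preferred-term tables can spread a handful of events over several rows.

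**Working it through.** The plan states no figure on this point that could be reproduced, so the main check is a comparison of the sections.

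| Item | Needs a scan? | Data collected in | Endpoint defined for | What the others get |
|---|---|---|---|---|
| BMD, BMC and their Z-scores | Yes | DXA substudy | DXA substudy | Nothing, by design |
| Height and weight Z-scores | No | All subjects | DXA substudy (synopsis, 2.2.1, 8.5.5) | Raw change only (8.5.6) |
| Clinical fractures, as a dedicated endpoint | No | All subjects (6.3) | DXA substudy (synopsis, 2.2.1); not in the 8.5.5 list | General adverse event tables (8.5.2) |

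**Who is left out.** There are two groups: subjects aged 10 to 13 at entry to the preceding study, and subjects aged 6 to 9 or 14 to 17 who did not join the substudy. The restriction is substudy membership, so the gap is wider than one age band.

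**How many.** The documents give the planned enrolment (415, section 3) but neither the age distribution nor the size of the DXA subgroup. Taking the share aged 10 to 13 as an assumption:

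- 20%: 415 × 0.20 = 83
- one third (ages even over 6 to 17, 4 of 12 single years): 415 × 4/12 ≈ 138
- 45%: 415 × 0.45 ≈ 187

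These are the subjects without a Z-score analysis on age alone. Non-participants in the two DXA age bands add an unknown number.

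**Scan interval (secondary).** DXA subgroup members who withdraw after Visit 12 are asked to have their final scan at an early Visit 16 (section 6.1.1), and section 8.5.5 states percent change without mentioning the interval. Suppose the scans are pooled, change is linear in time, and 20% withdraw evenly between Months 3 and 9. The mean change, as a fraction of the full-interval change, is 1 − 0.20 × (1 − mean early interval / full interval):

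- Baseline at Visit 9: mean early interval 6 of 9 months, so 1 − 0.20 × (1 − 6/9) = 0.933, about 7% too small.
- Baseline at the preceding study's Screening, assumed 2 + 12 = 14 weeks before Visit 9: intervals run from 14 + 12 = 26 to 14 + 36 = 50 weeks, mean 38, so 1 − 0.20 × (1 − 38/50) = 0.952, about 5% too small.

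The 20%, the linearity and the pooling are all assumptions, and section 8.5.5 does not define the DXA baseline. The result shows only that the effect would be small.

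**The case against.** The strongest reply concerns fractures. A reader might infer from the nesting that children aged 10 to 13 have no fracture assessment, or that their fracture data are discarded. The documents do not support that. Fractures are captured as adverse events in everyone, the Safety population is every dosed subject, and adverse event incidence by preferred term is the first listed safety endpoint.

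It would also be tempting to measure the loss by the precision of a zero count. The one-sided 95% upper bound, 1 − 0.05^(1/n), is 0.72% for n = 415 and 2.95% for an assumed subgroup of 100. That contrast would be the cost only if fractures outside the subgroup went unreported, and they do not. What remains is the lack of a grouped fracture incidence outside the subgroup and its omission from the section 8.5.5 list.

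Second, sections 8.5.5 and 8.6.1.1 defer details to an SAP whose text is not in the supplied document. It may already analyse Z-scores more widely or deal with scan intervals. That limits confidence, but the endpoint definitions in the synopsis and section 2.2.1 would still need correcting to match. Pooling of early and on-schedule scans is likewise an inference, so a reader should not conclude that the DXA result is biased by a known amount. The planned BMD Z-scores are also age-standardised.

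Third, Z-scores can be derived later from the stored data, so nothing is lost for good. That is true, but it is better to specify the main growth-safety analysis in advance than to add it after results are seen.

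**Conclusion.** The point holds for height and weight Z-scores and, in a narrower form, for fractures. The plan restricts both endpoints to DXA substudy participants, and its stated reason covers only the scan. Everyone else has a growth analysis that cannot show impaired growth, and fracture reporting that is complete but may be fragmented.

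The size is uncertain: about 83 to 187 of 415 subjects without a Z-score analysis on age alone, if 20% to 45% are aged 10 to 13, plus an unknown number of non-participants in the other two bands. The scan-interval issue is secondary, 5% to 7% under assumed conditions, and supports a sensitivity analysis only. The conclusion rests on the protocol text; an SAP with a wider growth analysis would reduce the point to aligning the protocol with it.

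**What to change.** 1. Take height and weight Z-score change out of the DXA bullet in the synopsis and section 2.2.1, and out of section 8.5.5. Report it for the full Safety population, overall and by age band (6 to 9, 10 to 13, 14 to 17), and name the growth reference and the baseline.
2. Define one grouped clinical-fracture incidence, with the preferred terms that it includes. Report it in the same population and age bands, and add it to section 8.5.
3. Keep only the BMD and BMC endpoints, with their Z-scores, in the DXA subgroup.
4. As a sensitivity analysis, show BMD and BMC change restricted to scans in the Visit 16 window, or annualised by the actual scan interval.

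The cost is a few derived variables and extra tables from data already collected. No subject undergoes a new procedure, and the number of DXA scans is unchanged.

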2.2.2 Efficacy

The efficacy endpoints are as follows:

- Overall and monthly changes from baseline in BM and SBM frequency rate
- Overall and monthly assessments of the average degree of, and changes from baseline in:
 - Stool consistency of SBMs
 - Straining associated with SBMs
 - Abdominal pain associated with SBMs
 - Constipation severity
- Monthly SBM Response
 - A monthly responder is defined as a subject who is a weekly responder for 3 of 4 weeks per month.

- A weekly responder is defined as a subject who has a frequency rate of ≥ 3 SBMs/week and an increase from baseline of ≥ 1 SBM/week for that week.
- Overall and monthly assessment of average treatment effectiveness rating
- Overall Health-related quality of life (PedsQL™)
- Overall and monthly change from baseline in incontinence episodes frequency (analysis performed for subset of subjects presenting with incontinence at baseline)
- Overall and monthly change from baseline in the production of large diameter stool (a stool that clogs the toilet) frequency
- Overall and monthly change from baseline in frequency of faecal impaction
- Overall and monthly change from baseline in proportion of BMs and SBMs in toilet overall
- Overall and monthly change from baseline in frequency of retentive posturing or excessive volitional stool retention

